#### 5.2.2.3 *Collection and Handling of Specimens*

- **Before the start of the pharmacokinetic studies:**

Sites should contact the [name] Laboratory at St. Jude Children's Research Hospital at [REDACTED] to request a Pharmacokinetic Kit for each patient enrolled on the study. The Pharmacokinetic Kit will provide the material to enable collection of samples.

- **During the pharmacokinetic studies:**

[figure not shown]
At each time-point, collect 0.5 mL of CSF in a screw-top tube along with concomitant plasma sample. Record the exact time that the CSF and plasma samples were obtained along with the exact time of drug administration on the CSF Pharmacokinetic DCF located on the PBTC-056 Protocol Webpage. Samples should be labeled with the PBTC study number, PBTC Accession Number, sample type, collection date, corresponding study timepoint (e.g., C1D1), and collection time. Samples should be stored at -80°C until shipped. All the information on the DCF should be filled out, and the DCF must be included in the shipment with the pharmacokinetic specimens collected.

Further information regarding the sample collection, processing and shipping will be found in the Pharmacokinetic Collection, Processing & Shipment Manual available on the PBTC-056 Protocol Webpage.

#### 5.2.2.4 *Shipping of Specimens*

Samples should be shipped for delivery Monday through Thursday with a generous amount of dry ice enclosed to safeguard against shipping delays. Weekend and holiday deliveries should be avoided. Samples should be shipped within 30 days of the last sample being taken. The site should use the PBTC-056 PK FedEx account details, located on the PBTC member website. Ship all pharmacokinetic samples along with the completed Pharmacokinetic DCF to:

[name] Laboratory

### 5.3 Exploratory Correlative Studies

#### 5.3.1 PBTC Central Review and Biorepository (PBTC CRB) Pathology and Exploratory Correlative Studies

The Pathology Central Review and Biorepository (PBTC CRB)'s function is to collect, distribute, and store specimens for pathology review and planned correlative studies which support the laboratory objectives of this protocol. **If the patient does not consent to participation in the repository, other correlative study samples should be submitted following the guidelines in the appropriate correlative study section.**

The CRB will also serve as a central repository for specimens collected for future research and leftover specimens (tumor tissue or blood) returned to the repository following the planned analysis from patients who consent to future research studies. These samples will be stored in the repository for undefined future studies which support the mission of the PBTC. **If the patient does not consent to future research, remaining correlative study samples will be destroyed once the PBTC-056 analysis is complete.**

##### 5.3.1.1 PBTC CRB Submission Guidelines

If the patient consents to provide slides for submission to the repository at the time of participation in a PBTC trial the following should be submitted:

- Tumor material

Slides from the original and/or recurrent surgery should be prepared for storage. The site should provide up to twenty (20) unstained sections cut at 4  $\mu$ m in thickness on (+) slides from the most representative section. Fewer unstained sections may be submitted based on size and availability of tissue. Preference is for tissue that has not previously been frozen. The corresponding pathology report(s) including immunohistochemical, special stains, and molecular/genetic results are to be uploaded to the PBTC using the secure File Upload system. These reports will be made available to the pathologist via a link in ProtoLab.

Suitability of sections would be established by preparing one (1) H&E to ensure that the sections meet the following criteria:

- histologically representative of the reported lesion
- contain at least 60% viable tumor
- no more than 40% necrosis

- Peripheral Blood Mononuclear Cells (PBMCs)

PBMCs may be collected by processing a 2–5mL whole blood specimen with Ficoll or collecting the specimen in a BD Vacutainer™ CPT™ Cell Preparation Tube with Sodium Citrate or similar tube which is available locally. Once separated, all pellets must be snap frozen and stored at least at -20°C prior to dry ice shipment

#### 5.3.1.2 *Specimen Collection*

- Processing by Ficoll tube

1. Collect 2–5mL of fresh blood into an EDTA tube.
2. Transfer blood into a sterile 50 mL tube and add double the amount of PBS. MIX GENTLY.
3. Set up another tube containing half of its total volume of Ficoll. For example, if there is 15 mL of blood + PBS, then use 7.5 mL of Ficoll (2:1 ratio).
4. At very slow pace (approx. 2 mL/minute), layer the blood + PBS mixture onto the Ficoll so that the solutions DO NOT MIX. Spin the blood/Ficoll at 750 g in slow mode for 30 minutes @ 25°C. After spin you will see four distinct layers: plasma (top layer), white fluffy ring (2nd layer), Ficoll (3rd layer), and blood (bottom layer).
5. Remove plasma layer down to about 1 mL above the white fluffy ring and discard.
6. Collect the entire white fluffy ring. If ring is hard to see, also take extra liquid above. Then discard everything else.
7. Place this fraction of white blood cells into a fresh 50 mL sterile tube with 20 mL of PBS. Spin down for 10 minutes @ 25°C, 750 x g in fast mode. Remove the supernatant. Add back to pellet 1 mL of PBS and spin for 5 min. at 4°C at 10,000 rpm. Remove supernatant.
8. Freeze the pellet of WBCs in a 2 mL cryovial and store at -80°C until shipment. Cryovials larger than 2 mL cannot be accepted by the PBTC CRB.
9. Please ensure that the labeling system used is designed to withstand temperatures down to -80°C. Samples should be stored at -80°C until shipment. For short term storage (2–3 weeks) -20°C is acceptable. NOTE 4°C IS NOT ACCEPTABLE STORAGE.

If it is not possible to collect the PBMC by Ficoll gradient then separation of PBMC can be conducted using CPT tube separation as an alternative. However, the PBMC pellet MUST BE frozen immediately and stored at -80°C.

- *Collection and Processing by CPT tube*

1. Peripheral blood should be collected in a BD Vacutainer CPT™ Cell Preparation Tube with Sodium Citrate or similar tube which is available locally. 8 mL and 4 mL CPT tubes can be obtained from Fisher Scientific (Cat# 02-685-125, 02-688-81) or Becton-Dickinson (BD No.362761, 362760). The 8 mL tubes have a 6 mL minimum draw and the 4 mL tubes have a 3 mL minimum draw.
2. Centrifuge the CPT™ tube at 1500 x g for 30 minutes at room temperature (20°C to 25°C). DO NOT APPLY THE BREAK ON THE CENTRIFUGE. Use acceleration 5, brake 0 (“slow mode”).
3. It may be necessary to spin the tube longer to ensure that all of the red blood cell

components have been separated from the plasma layer through the polyester gel barrier.

4. The tube should be removed immediately from the centrifuge. The mononuclear layer and plasma lie above the polyester gel plug.
5. Using a sterile pipette, remove as much of the plasma component (upper half of the CPT tube) without disturbing the mononuclear layer if possible and discard.
6. Transfer mononuclear cell layer (and some residual plasma layer) to a labeled 15 mL conical centrifuge tube and add 5 mL sterile room temperature magnesium or calcium-free phosphate buffered saline (PBS) to fill the conical tube and recap.
7. Centrifuge at 450 x g for 10 minutes at room temperature (20°C to 25°C). Use acceleration 9, brake (“fast mode”).
8. Remove supernatant, being careful not to aspirate the cellular pellet at the bottom of the tube.
9. Add 1 mL of sterile PBS to the pellet and gently re-suspend by pipetting up and down. Transfer the entire suspended pellet to the labeled 2 mL cryovial. Cryovials larger than 2 mL cannot be accepted by the PBTC CRB.
10. Centrifuge the cryovial at 450 x g for 5 minutes (or spin down the microcentrifuge tube at 1300 x g for 5 minutes) at room temperature. Discard the supernatant. Store the cell pellet cryovial frozen at -80°C. For short term storage (2–3 weeks) -20°C is acceptable.

#### 5.3.1.3 *Handling of Specimens*

All samples should be labeled with the following:

- Patient PBTC Accession #
- PBTC study #
- Collection date
- Slide number (For slides only; designate as “PBTCR #” where the # is assigned from 1 to 20 or the highest number of unstained sections prepared, sequentially) **or** “PBTCR H&E” for the H&E stained section.

Slides, scrolls, and Formalin Fixed, Paraffin Embedded (FFPE) tumor material should be shipped at room temperature. PBMCs should be shipped with a generous amount of dry ice enclosed to safe guard against shipping delays.

#### 5.3.1.4 *Shipment of Specimens*

The sample collection, shipping dates and tracking number(s) must be documented in the eCRF. Samples collected for the repository should be sent to the PBTC CRB via FedEx by completing the internet form at <http://www.fedex.com/us/> and requesting FedEx to email [REDACTED]. FedEx user ID and password for pathology shipping can be found on the PBTC-056 Protocol Webpage. Samples are to be shipped to:

PBTC CRB

[REDACTED]  
[REDACTED]  
[REDACTED]  
[REDACTED]

### 5.3.2 Pathology Central Review

Retrospective central pathology review will be completed from the slides submitted to the PBTC CRB if the patient consents to the CRB. Pathologist review of slides submitted to the PBTC CRB will include the following elements:

- Examination of H&E stained slides: For each subject, one (1) H&E stained slide per one representative block from the brain tumor, removed either at initial diagnosis or relapse, should be submitted for review.
- Review of the corresponding pathology report(s) of the immunohistochemical, special stains, and molecular/genetic results from current and/or original primary tumor
- If necessary, review of immunohistochemical or special stained slides. Slides submitted to the PBTC CRB will be digitized to 40X. H&E stained sections will be retained and filed at the CRB. Original immunohistochemical or special stain slides will be returned to the submitting institution.

### 5.3.3 Serum Pharmacodynamics Study: HER2 ECD

Serum pharmacodynamic studies are mandatory and will be obtained from all patients enrolled on this study.

#### 5.3.3.1 *Collection of Specimens*

The blood samples for INCB007839 pharmacodynamic (PD) studies will be collected at the following timepoints:

- Pre-dose
- Course 1 Day 14 ( $\pm$  2 days)

#### 5.3.3.2 *Handling of Specimens*

At each time point, 2 mL of blood will be collected into appropriate BD Vacutainer red-top tube. The Pharmacodynamic Data Collection Form (DCF) should be completed with the exact time that the sample is drawn as well as the exact time that the drug is administered. The PD DCF is located on the PBTC-056 Protocol Webpage.

Instructions for serum processing:

- 1) Allow vacutainer to fill completely.
- 2) Gently invert the vacutainer approximately 5 times to allow complete mixing of additive.
- 3) Allow sample to clot at room temperature.
- 4) Centrifuge to separate the clot from the serum (refrigerated centrifuge is recommended but not required).
  - a. Spin at 1200 x g for 10 minutes.
- 5) Remove the stopper of the vacutainer.
- 6) Using a pipette, aliquot serum into screw top tube for shipping.
- 7) Samples should be labeled with the PBTC Study #, PBTC Patient Accession #, collection date, and the Course, Day, and Time information for each sample. Store samples at -80°C

until shipment.

#### 5.3.3.3 *Shipping of Specimens*

At the start of the study, each participating institution will receive a Pharmacodynamics (PD) Kit from [name] for the collection of samples.

Samples should be shipped for delivery Monday through Thursday with a generous amount of dry ice enclosed to safeguard against shipping delays. Weekend and holiday deliveries should be avoided. Sites should contact the [name] Laboratory at Stanford University, at [REDACTED] to request a Pharmacodynamics Kit for each patient enrolled on the study.

Samples should be shipped within 30 days of the last sample being taken. The site should use the PBTC-056 FedEx account details located on the PBTC-056 Protocol Webpage. Ship all pharmacodynamic samples on dry ice, along with a completed Pharmacodynamics DCF to:

[name] Laboratory

[REDACTED]  
[REDACTED]  
[REDACTED]  
[REDACTED]  
[REDACTED]

Samples must be shipped from the site to the respective laboratory within 30 days of last sample collection in order to receive cost reimbursement. The sample collection and shipping dates must be documented in the eCRF.

#### 5.3.4 Exploratory Pharmacodynamics Study: NLGN3 in CSF samples

In consenting patients, this exploratory correlative study will monitor CSF NLGN3 levels by western blot in optional lumbar punctures or ventricular/Ommaya taps before and after initiation of therapy.

##### 5.3.4.1 *Collection & Handling of Specimens*

CSF samples will be collected after study enrollment at the time of any lumbar puncture or shunt tap from an Ommaya as clinically indicated.

##### 5.3.4.2 *Shipping of Specimens*

Undiluted, frozen CSF samples should be shipped for delivery Monday through Thursday with a generous amount of dry ice enclosed to safeguard against shipping delays. Weekend and holiday deliveries should be avoided.

Samples should be stored at -80°C and shipped as soon as possible. The site should use the PBTC-056 FedEx account details, located on the PBTC-056 Protocol Webpage. Ship all CSF samples on dry ice to:

[name] Laboratory

**5.4 Neuroimaging Studies**

Patients will have MRI brain (for primary brain HGG) or MRI spine (for primary spinal cord HGG) with and without contrast performed at the following timepoints:

- Prior to therapy
- After Courses 2, 4, and 6
- After Courses 9, 12, 15, 18, 21, and 24 (approximately every 12 weeks)
- Post-therapy (after Course 26)

MRI spine should be performed prior to therapy and at the same time points as standard MRI brain, if clinically indicated. For primary spinal HGG, brain imaging should only be performed as clinically indicated. See [Section 11](#) for details.

Standard MR imaging will include Sagittal T1 MPRAGE, axial DWI, axial T2 FLAIR, axial T2, and post gadolinium sagittal T1 MPRAGE (with reconstructions) images. The standard MR parameters are listed on the PBTC NIC web page located at <http://www.childrenshospital.org/research/centers-departmental-programs/pediatric-brain-tumor-consortium-neuroimaging-center> under Neuroimaging Studies/ Specific MR Imaging Sequences- Open PBTC Protocols. There is also a link to the same PBTC-NIC webpage from the PBTC-056 Protocol Webpage.

Volumetric analyses will be done at the Neuroimaging Center (NIC, Children's Hospital Boston) via the Vitrea (VitreaTM) workstation, from the axial T2 FLAIR and T1 -weighted post-contrast brain images.

**5.4.1 Neuroimaging Review**

Local review of MR imaging studies will be performed at each site and central review of the MR imaging studies will be conducted through the PBTC Neuroimaging Center (NIC). NIC review will include assessment of response to therapy (as feasible). The director and one neuroradiologist of NIC will review the imaging studies at study completion. If the local and central review are not in agreement, the NIC neuroradiologist will confer with the participating site to determine why there is a discrepancy via conference call.

For patients whose MRI scans suggest a response, a confirmation scan should be obtained approximately 8 weeks later. This scan, as well as the baseline and best response scans, will be electronically transferred to the PBTC Neuroimaging Center (NIC) for central review at the

completion of the study. All patient specific data are stripped from the images and replaced with PBTC Accession numbers prior to transmitting the images to the NIC. All image data transfer is accomplished using PGP (pretty-good-privacy) 128-bit encryption which meets industry standard for secure communication.

## 6.0 TREATMENT PLAN

Treatment can be administered on an outpatient basis. Reported adverse events and potential risks are described in [Section 10](#). Appropriate dose modifications are described in [Section 7](#). No investigational or commercial agents or therapies other than those described below may be administered with the intent to treat the patient's malignancy. Alternative therapies such as cannabinoids (cannabis oil, THC, etc.) will not be allowed.

Timing of protocol therapy administration and response assessment studies are based on schedules derived from the experimental design or on established standards of care. Minor unavoidable departures from protocol directed therapy and/or disease evaluations for valid clinical, patient and family logistical, or facility, procedure and/or anesthesia scheduling issues are acceptable and should be documented. Contact a Study PI and the responsible Protocol Coordinator if there are any questions.

### 6.1 Agent Administration

This is a phase 1 dose finding trial in pediatric patients with recurrent/progressive high-grade glioma, including DIPG and other diffuse high-grade gliomas.

Given that the adult RP2D was 200 mg PO BID, we plan to evaluate the safety and tolerability of approximate pediatric equivalent dose based on a typical adult size of  $1.67 \text{ m}^2$ . Thus, we propose to start at  $120 \text{ mg/m}^2$  and de-escalate to  $80 \text{ mg/m}^2$  if this dose is not tolerable.

INCB007839 is administered orally (PO), twice a day each day for 28-day cycles. A medication diary will be required to ensure appropriate drug administration ([Appendix C](#)). The patient will be requested to maintain the medication diary documenting each dose of medication. The medication diary will be returned to clinic staff at the end of each course.

Given the known risk of thrombosis associated with INCB007839, DVT prophylaxis is required with low molecular weight heparin (LMWH, e.g., enoxaparin at 1 mg/kg/day [can be divided BID] with a maximum dose of 40 mg/day), with a goal of anti Xa level of 0.3–0.5 units/mL. DVT prophylaxis should continue throughout the duration of treatment and for 2 weeks after cessation of study drug, except as noted below.

- If a contraindication to DVT prophylaxis occurs (e.g., a new injury at risk of bleeding, planned invasive procedures, allergy to pork products, etc.), the study drug should be held at the time of LMWH cessation. LMWH should be held in these instances per institutional standards or the treating physician's discretion if no guidelines exist. If the temporary risk of anti-coagulation resolves, patients may restart INCB007839 with concurrent LMWH at the discretion of the treating physician.

**Table 3. Dose De-escalation Schedule**

Dose Level	INCB007839 dose (mg/m  /dose, PO, BID)	BSA Range
0 #	80 mg/m  /dose BID	0.55–2.80 m 
1 *	120 mg/m  /dose BID	0.70–2.50 m 

# Patients on Dose Level 0 who have a BSA of 0.55–1.0 m^2 will only receive the AM dose.

\* Starting Dose

**Table 4. Course 1 Dosing Schedule**

BID Dosing*	Day 1	Day 2	Day 3–28
AM Dose	Yes	No	Yes
PM Dose	No	No	Yes

\*Patients will be asked to hold the second dose on Day 1 and the two doses on Day 2 of Course 1 for plasma PK studies. The AM dose on Day 3 must be administered AFTER the collection of the PK sample (48-hour).

#### 6.1.1 INCB007839

INCB007839 is supplied as 100 mg sustained release tablets. Patients will receive INCB007839 orally twice a day each day for 28-day cycles. Patients may continue to receive INCB007839 on study for up to 26 courses (approximately 2 years) in the absence of disease progression or unacceptable toxicity. Enrolled patients will be followed after completion of study therapy for 2 years or death, whichever occurs first. Delays between courses for reasons other than toxicity may occasionally occur, however, dosing should follow the treatment plan as closely as possible. Discuss and document any protocol deviations with the Study Chair. Duration of therapy is defined in [Section 6.4](#).

Dosing should be adjusted based on body surface area (BSA) calculated at the beginning of each course of therapy. The dose prescribed should be rounded to the nearest deliverable dose based on the BSA adjustment and the available pill size. Dosing tables which reflect this approach are available in [Appendix B](#). Patients will be provided with a medication diary for INCB007839, instructed in its use, and must bring the diary as well as the remaining pill bottles with them to each appointment. The medication diary is in [Appendix C](#).

As much as possible, INCB007839 should be taken without food (1 hour before meals or 2 hours after), with water rather than other fluids. Dosing is every 12 hours ( $\pm$  2 hours), but if a dose is not given within 4 hours, consider it missed. If a dose is missed, it should be documented in the diary and the next scheduled dose should be taken as scheduled. Patients who vomit a dose of INCB007839 should NOT be re-dosed, and appropriate anti-emetic therapy should be implemented prior to the next scheduled dose.

#### 6.1.2 Criteria to start subsequent courses

A course may be repeated every 28 days if the patient has at least stable disease and has again met laboratory parameters as defined in [Section 3.1.9](#), and [3.1.14](#) if applicable.

- If a patient does not meet these parameters at the end of the dose-finding period, then

INCB007839 should be held until parameters meet the criteria. If parameters are not met within 7 days of the scheduled course to begin, this is a dose-limiting toxicity (see [Section 6.2](#)) and dose reduction is indicated.

- If a patient does not meet these parameters at the end of subsequent courses (i.e., Course 2 and onward), then INCB007839 should be held until parameters meet the criteria. If parameters are not met within 7 days of the scheduled course to begin, this will require a dose modification (see [Section 7.0](#)).
- If INCB007839 is held for any reason other than toxicity (e.g., planned procedure), it can be restarted (with concurrent anti-coagulation) at the same dose and with counting of course days continuing (e.g., if INCB007839 is held on Days 13–16 of a course due to a shunt revision, restart INCB007839 and LMWH on Day 17 and continue counting course days for a 28-day course).

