## 6.2 Definition of Dose-Limiting Toxicity (DLT)

DLT will be defined as any of the events listed in this section that are at least possibly related to the investigational agent and that occur during the dose-finding period regardless of expectedness.

- Any INCB007839-related adverse event during the first course of therapy that leads to a dose reduction or results in the permanent cessation of therapy will be considered dose limiting. All dose modifications in all courses are to follow the guidelines provided.
- Any INCB007839-related adverse event during the first course of therapy that results in a delay of treatment > 7 days.

6.2.1 Non-hematologic dose limiting toxicity is defined as:

- Any Grade 4 non-hematologic toxicity
- Any Grade 3 non-hematologic toxicity with the exception of:
  - Grade 3 nausea and vomiting of < 5 days and responsive to anti-emetic treatment
  - Grade 3 elevation of transaminases that returns to levels meeting eligibility criteria within 7 days of study drug interruption and does not recur upon restarting drug.
  - Grade 3 fever or infection of fewer than 5 days in duration
  - Grade 3 hypophosphatemia, hypokalemia, hypocalcemia, or hypomagnesemia responsive to oral supplementation
- Any Grade 2 non-hematologic toxicity that persists for > 7 days and is considered medically significant or sufficiently intolerable by the patient that the toxicity requires treatment interruption
- Any deep venous thrombotic event (superficial phlebitis is excluded unless Grade 3 or 4 as above)
  - If a patient on this study has a thrombotic/thromboembolic event that is not related to the central line, treatment with INCB007839 will be discontinued and not restarted. Determination of attribution will be reviewed by the study team and discussed with PBTC Toxicity Committee and CTEP; and such events will be reported to the CTEP-AERS, PBTC DSMB, and the FDA as events of special interest in an expedited fashion. See special reporting requirements in [Section 10.3](#). In this event, enrollment will be halted until fully reviewed. In addition, any patient experiencing a non-central line-related thromboembolic event should have the

studies listed below performed as soon as possible after the event.

- Patients with a venous thrombosis should have the following assessed as soon as possible after thrombosis is suspected/confirmed:
  - CBC
  - Antithrombin
  - Protein C
  - Protein S
  - Factor V Leiden
  - Prothrombin G20210A gene analysis

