#### 6.2.3 Dose-finding period

The dose-finding period begins with the initial dose of INCB007839 and ends on the last day of Course 1. Should there be a delay starting the subsequent course, dose-finding will complete on the start date of Course 2.

Management and dose modifications for toxicities which occur outside of the dose-finding period should also follow guidelines in [Section 7](#), however, these will not be considered dose limiting for the purpose of dose finding.

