#### 6.2.4 Dose De-escalation

Dose de-escalation will proceed as follows:

- Course 1 will be started with an initial cohort of six (6) patients at  $120 \text{ mg/m}^2/\text{dose BID}$  (the dose levels to be tested are listed in [Table 3](#)). If more than 1 DLT is observed in 6 patients treated at Dose Level 1, de-escalation to Dose Level 0 will occur as outlined in

[Section 9.1](#). Only DLTs observed during the dose finding period of therapy will be used to guide dose de-escalation. Patients treated at Dose Level 0 who have a DLT will discontinue study therapy.

- If thrombosis occurs outside of the DLT period, this will be discussed with study team to determine attribution to study drug, potential dose-association, as well as consideration of the risk/benefit ratio of prophylaxis in subsequent patients.
- Patients enrolled on Dose Level 1 who have a dose-modifying toxicity outside of the dose-finding period (e.g., in Courses 2 and onward) should have the dose of INCB007839 reduced on subsequent courses to Dose Level 0. Patients can begin the subsequent course at the lower dose when the toxicity has resolved to Grade 1 or baseline and laboratory parameters are met as defined in [Section 3.1.9](#) and [3.1.14](#). Patients enrolled on Dose Level 0 who require a dose reduction will not receive further treatment on study and will be considered off treatment (see [Section 6.4.2](#)).

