### 7.1.2 Dose Modification for Non-thromboembolic Toxicity

A patient who has a non-thromboembolic toxicity at 120 mg/m^2 or is delayed > 7 days from the planned start of the next course should be dose reduced to 80 mg/m^2 on subsequent cycles. A patient who has a non-thromboembolic toxicity at 80 mg/m^2 or is delayed > 7 days from the planned start the next course will not receive further treatment on study and will be considered off treatment (see [Section 6.4.2](#)).

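### Section 6.1.2 counts a failure to meet restart laboratory parameters within 7 days after Course 1 as a DLT whatever its cause, whereas Section 6.2 counts only events at least possibly related to INCB007839

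*Combined protocol and SAP*

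**What the plan says.** Section 6.1.2 allows a new course if disease is at least stable and the laboratory parameters of Section 3.1.9 (and 3.1.14 for HIV-positive patients) are met again. Its first bullet covers the end of Course 1: "If a patient does not meet these parameters at the end of the dose-finding period, then" the drug is held until the criteria are met. It continues: "If parameters are not met within 7 days of the scheduled course to begin, this is a dose-limiting toxicity". A pointer to Section 6.2 follows, and the sentence ends by calling for a dose reduction. The third bullet covers other holds: "If INCB007839 is held for any reason other than toxicity (e.g., planned procedure), it can be restarted" at the same dose, with anticoagulation.

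Section 6.2 opens with the general definition: "DLT will be defined as any of the events listed in this section that are at least possibly related to the investigational agent". Its item on delay reads: "Any INCB007839-related adverse event during the first course of therapy that results in a delay of treatment > 7 days".

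Section 6.2.3 sets the window: "Should there be a delay starting the subsequent course, dose-finding will complete on the start date of Course 2". Section 6.2.4 adds: "Only DLTs observed during the dose finding period of therapy will be used to guide dose de-escalation". Sections 6.2.4 and 9.1 de-escalate from Dose Level 1 if more than 1 DLT is seen in the first 6 patients. Section 9.1 considers de-escalation if more than 3 are seen in 12.

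Section 7.1.2 has its own delay rule. A patient with a non-thromboembolic toxicity at the higher dose "or is delayed > 7 days from the planned start of the next course should be dose reduced to" the lower one. The delay clause has no attribution condition.

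**The concern.** Estimating the MTD or RP2D is a primary objective (Section 1.1.2), and the whole decision rests on a count of DLTs in six and then twelve patients. An event whose DLT status depends on which section is open makes that count ambiguous.

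Such an event is possible. The 3.1.9 parameters include thresholds for platelets, neutrophils, liver enzymes and creatinine; 3.1.14 adds CD4 count and viral load for HIV-positive patients. These patients have recurrent disease and prior therapy, so a value can stay out of range for reasons other than the study drug. Section 10.2 provides the attributions unlikely and unrelated for such cases.

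The classification also affects the individual patient. Under 6.2.4, a DLT at Dose Level 0 ends study therapy.

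**Working it through.** **Text comparison.** Take a patient who completes Course 1, has a laboratory value outside the restart criteria for more than 7 days, and whose abnormality is attributed as unlikely or unrelated.

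- *Section 6.1.2, first bullet, read literally:* DLT. The only conditions are the failed parameter and the 7 days.
- *Section 6.2:* not a DLT. The general definition requires at least a possible relation, and the delay item requires a related adverse event.
- *Section 6.2.3:* the delay falls inside the dose-finding period, which stays open until Course 2 starts.
- *Section 12.1:* a patient with at least 45 of 53 doses (45/53 = 84.9%; 23 of 27 for the once-daily group), completed monitoring and no confounding treatment is evaluable. The patient is then in the denominator on both readings, and only the numerator differs.

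The 7-day limits agree, and events rated possible, probable or definite raise no attribution conflict. The divergence is confined to the unlikely and unrelated categories.

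**Effect on the first decision.** With exactly one other DLT among the six, the count is 1 under 6.2 (expand) and 2 under 6.1.2 (de-escalate). With no other DLT, one such patient changes nothing. With two or more others, the dose is left on either reading.

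**Illustration of size.** The plan states no operating characteristic that depends on this point, so there is no figure to reproduce. Both rates below are assumptions:

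- p = probability of a related DLT
- q = probability of an unrelated laboratory failure lasting more than 7 days, independent of p

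Under 6.2 the counted rate is p. Under literal 6.1.2 it is r = 1 − (1 − p)(1 − q). The first gate is P(more than 1 in 6) = 1 − (1 − r)^6 − 6r(1 − r)^5.

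At p = 0.10:

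- q = 0: r = 0.10; 1 − 0.531 − 0.354 = 0.114
- q = 0.03: r = 1 − 0.90 × 0.97 = 0.127; result 0.171
- q = 0.05: r = 1 − 0.90 × 0.95 = 0.145; result 0.212
- q = 0.10: r = 1 − 0.90 × 0.90 = 0.19; result 0.320

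The same calculation at other related-DLT rates:

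| p | q = 0 | q = 3% | q = 5% | q = 10% |
|---|---|---|---|---|
| 5% | 0.033 | 0.075 | 0.109 | 0.212 |
| 10% | 0.114 | 0.171 | 0.212 | 0.320 |
| 15% | 0.224 | 0.285 | 0.326 | 0.430 |
| 20% | 0.345 | 0.403 | 0.442 | 0.536 |

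The second gate adds the chance of passing the first with x = 0 or 1 DLTs and then seeing at least 4 − x in the next six. The total probability of crossing either threshold at p = 0.10 is 0.121 for q = 0, and 0.184, 0.231 and 0.359 for q = 3%, 5% and 10%. At p = 0.20 it is 0.388, then 0.458, 0.505 and 0.615. This takes the expanded cohort as exactly 12, although the plan says at least 12.

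**The case against.** The best defence is the pointer. The 6.1.2 sentence refers the reader to 6.2, which is the titled DLT definition, uses the same 7-day limit and reads as a closed list. On that view 6.1.2 only restates the delay item, and an unrelated failure is not a DLT. This is a plausible reading and perhaps the intended one. But 6.1.2 states the classification flatly, and no text says that 6.2 governs.

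The plan also separates toxicity from other delays elsewhere. Section 6.1.1 foresees delays between courses for other reasons, and the third bullet of 6.1.2 allows a same-dose restart after a non-toxicity hold. A reader might therefore infer that every unrelated delay becomes a DLT under 6.1.2. The documents do not support that: a hold for a planned procedure has its own bullet, and the conflict concerns failed laboratory parameters only. Yet the third bullet does not say that it overrides the first. If it does apply to an unrelated laboratory failure, 6.1.2 gives two different dose instructions for the same patient.

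The affected group is small. There are no earlier pediatric studies (Section 2.2.3), so many abnormalities would probably be rated at least possible and count either way. Hemoglobin may be supported by transfusion. Sites must send source documents supporting DLT status to the consortium (Section 13.3), so the classification is not the site's alone. All this lowers the likely frequency, but it does not say which rule a central review would apply.

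**Conclusion.** The inconsistency is real and narrow. Two current provisions classify the same event differently, the event lies inside the DLT window, and the count feeds the primary decision. That conclusion needs no assumption about rates.

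The size does. With p = 10%, counting such events raises the probability of leaving Dose Level 1 at the first gate from 0.114 to between 0.171 and 0.320 for q between 3% and 10%. The effect is zero if they never occur.

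Three stronger conclusions are not supported:

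- *That the chance of leaving a tolerable dose doubles or triples.* At p = 10% the ratio is 1.5, 1.9 and 2.8 for q = 3%, 5% and 10%. At p = 15% it is 1.3, 1.5 and 1.9. The documents give no value of q, and the model assumes that every such event is counted despite 6.2.
- *That one reclassified patient by itself decides the dose.* At the first gate this needs exactly one other DLT.
- *That the trial would end at Dose Level 0.* Section 9.1 closes accrual and then reconsiders whether to amend or close permanently.

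The point deserves correction before dose decisions are made, but it does not undermine the design.

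**What to change.** Reconcile Sections 6.1.2 and 6.2 so that one rule decides whether a laboratory delay of more than 7 days after Course 1 counts as a DLT for the MTD decision. One way is a clause making the 6.1.2 sentence expressly subject to the general definition already in 6.2. If the sponsor means such delays to count whatever their cause, 6.2 must list them and state the exception to attribution.

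The same edit should reconcile three dose-modification statements: the dose reduction attached to the first bullet of 6.1.2, the same-dose restart in its third bullet, and the unattributed delay rule in 7.1.2. Which clinical rule is right is for the sponsor, and none is proposed here. Section 12.1 needs no change for this purpose, because it already makes a patient with sufficient dosing and completed monitoring evaluable.

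The cost is about one clause for the DLT count plus the dose-modification edit. The small downside of the suggested clause is that attribution must be adjudicated for these delays, as 6.2 already requires for other DLTs.
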